•	Primary endpoint will be assessed as per an intention-to treat principle	
•	Subsequent analysis will also be performed based on as treated	
	groups	
•	Pre-specified subgroup analyses will include:	
	Stent vs. non-stent groups	
	• DES vs. BMS	
	• Above and below-the knee treatment	
	Claudication vs. CLI groups	

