## 6. Trial endpoints

Clinical endpoints will be analyzed in all subjects who are enrolled, regardless of whether the trial treatment administered successfully completed for the desired duration. A subject will be considered enrolled in the trial when he/she is randomized to one of the treatment arms of the study. All endpoints are subject-based unless otherwise specified.

The primary endpoint is subject-based of the longer of a 12-month or end of study treatment endpoint of the first occurrence of index limb arterial occlusion, surgical intervention,

endovascular intervention, amputation of the affected limb (primary patency and limb salvage), MI, ischemic stroke or death (survival)

The secondary endpoints are subject-based on the longer of a 12-month or end of study treatment endpoints that include: (a) the first occurrence of any individual component of the primary endpoint, (b) the first occurrence of the following during follow-up: cardiovascular death, or MI, or ischemic stroke, or any amputation above the ankle and (c) severe bleeding defined according to the Global Utilization of Streptokinase and Tissue plasminogen activator for Occluded coronary arteries (GUSTO) classification

The tertiary endpoint is based on the longer of a12-month or end of study treatment moderate bleeding according to the GUSTO classification

Clinically indicated DAPT duration will be based on the longest pre-discharge following index peripheral intervention procedure DAPT duration. This will be determined based on: peripheral intervention device IFUs, preceding coronary intervention, acute coronary syndrome or other guideline-based clinical or device specific DAPT duration.

Study treatment will be discontinued at the first occurrence of a primary endpoint as defined in the table below. Patients, however, can resume taking aspirin, Clopidogrel, or both based on their provider's clinical decision.

Primary endpoint definition(s)	Secondary/Tertiary endpoint definition(s)
Occlusion of the target limb documented by any imaging procedure performed clinically	As described in section 6, except for:
any maging procedure performed ennearly	GUSTO bleeding criteria:
Any surgical or endovascular	1. Severe or Life-threatening: Intracerebral hemorrhage resulting in substantial
revascularization procedure on the index limb	hemodynamic compromise requiring treatment
Amputation above the ankle of the index	2. Moderate: Requiring blood transfusion but not resulting in hemodynamic

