## 9. Method of assigning subjects to treatment

Patients scheduled for a planned discharge will be randomized on a 1: 1 basis using a central computerized randomization portal available through RedCap® to either of the following treatment groups:

ASA (81 mg/d for U.S. sites; 75-100 mg for international sites) + clopidogrel:for clinically indicated duration with a minimum of 30 days (control arm)

ASA (81 mg/d for U.S. sites; 75-100 mg for international sites) + clopidogrel 75 mg: for clinically indicated duration + 12m (treatment arm)

An inclusion and exclusion checklist needs to be completed via computerized randomization portal available through  $RedCap^{(R)}$  prior to randomization of the subject.

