## **19. Statistical analysis**

Continuous variables will be summarized as mean±standard deviation and compared using the t-test or the Wilcoxon rank-sum test, as appropriate. Discrete variables will be presented as frequencies and group percentages and compared using the chi-square test. For all comparisons a two-sided probability of <0.05 will be considered statistically significant. All analyses were performed using the SAS 9.4 or recent version (SAS Institute Inc., Cary, North Carolina). Primary endpoint will be assessed as per an intention-to treat principle.

Subsequent analysis will also be performed based on per-protocol basis. Pre-specified

subgroup analyses will include:

- 1. Stent vs. non-stent groups
- 2. DES vs. BMS
- 3. Above and below-the knee intervention

4. Claudication vs. CLI groups

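### The Synopsis adds an undefined as-treated analysis; if subjects are grouped by duration received, stopping treatment at the first primary event biases this non-primary comparison towards long treatment

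*Combined protocol and SAP*

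**What the plan says.** In the Synopsis, under Statistical analysis: "Primary endpoint will be assessed as per an intention-to treat principle". The next item reads "Subsequent analysis will also be performed based on as treated" groups, with no rule for forming them. Section 19 covers the same ground but has "Subsequent analysis will also be performed based on per-protocol basis". Section 17 defines two analysis sets only, intent-to-treat and per-protocol; the latter is limited to subjects treated for their assigned duration.

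Section 9 describes arms that take the same two drugs and differ in length: "clinically indicated duration with a minimum of 30 days (control arm") against "for clinically indicated duration + 12m (treatment arm").

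Section 6 links exposure to outcome: "Study treatment will be discontinued at the first occurrence of a primary endpoint as defined in the table below". It adds: "Patients, however, can resume taking aspirin, Clopidogrel, or both based on their provider's clinical decision".

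Two horizons appear for the primary endpoint. The Synopsis and Sections 6 and 14 use the longer of 12 months or end of study treatment. Section 20, under Primary Endpoint, refers to a 12-month composite.

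**The concern.** Both arms start on the same drugs, so as-treated groups that differ from the randomised groups would ordinarily be formed by how long treatment was taken. Under Section 6, a primary event ends study treatment. A long-arm subject whose event falls within the clinically indicated period has therefore received only control-length study treatment. Grouped by duration received, that subject moves to the short group and takes the event along. Everyone left in the long group is event-free at the end of the indicated period by construction, which is immortal-time bias. No section provides a landmark, a time-dependent exposure, or an exception for treatment stopped because of an endpoint.

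At stake is how a secondary analysis reads beside the primary one. It could seem to support long treatment when the drug does nothing.

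**Working it through.** **The plan's own figures.** The plan gives no figure for the as-treated analysis. Its sample size does reproduce from 49% vs 34%, 80% power and two-sided 0.05. The two-proportion formula gives 169 per arm uncorrected and 182 per arm (364 in total) with continuity correction, against 368 evaluable stated. Then 364/0.90 = 404.4, rounded up to 405, against 404 randomised. So 49% is a fair planning rate to use below.

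**Inputs from the documents.** 49% control risk at 12 months (Synopsis); 202 per arm (Section 14); 1:1 allocation and the two durations (Section 9); treatment stop at the first primary event (Section 6).

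**Assumptions not in the documents.** No drug effect, so 49% in both arms; constant hazard; indicated duration c of 1, 3 or 6 months for everyone; long means any treatment beyond c. Dropout, other non-adherence and control subjects who continue past c are not modelled.

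**Formulas.**
- Share of the long arm that fails before c and moves: e = 1 − 0.51^(c/12)
- Short-group risk: (0.49 + e)/(1 + e)
- Long-group risk, cut at 12 months: 1 − 0.51^(1 − c/12)
- Long-group risk, followed to c + 12 months: event-free at c, then 12 further months, so 1 − 0.51 = 49%

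Example, c = 3: e = 1 − 0.51^0.25 = 15.5%. Short group = (0.49 + 0.155)/1.155 = 55.8%. Long group at 12 months = 1 − 0.51^0.75 = 39.6%.

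| c (months) | Long-arm subjects moved (202e) | Short group | Long group, cut at 12 m | False difference | Long group, to c + 12 m | False difference |
|---|---|---|---|---|---|---|
| 1 | 11 | 51.6% | 46.1% | 5.6 points | 49% | 2.6 points |
| 3 | 31 | 55.8% | 39.6% | 16.2 points | 49% | 6.8 points |
| 6 | 58 | 60.3% | 28.6% | 31.8 points | 49% | 11.3 points |

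Differences are taken before rounding. The last column is smaller because the long group has c more months in which to have an event, which works against it.

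**False positives at the 12-month cut.** In 5,000 simulated null trials per scenario, the as-treated test significantly favoured long treatment in about 20%, 90% and 100% of trials for c = 1, 3 and 6. The nominal rate in that direction is 2.5%. The same data analysed as randomised rejected in about 5% of trials, both directions together. The longer horizon was not simulated.

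**Hazard shape.** Constant hazard is not an upper bound. With an assumed early-loaded hazard, survival 0.51^√(t/12), and c = 1:
- e = 1 − 0.51^√(1/12) = 17.7%, so the short group is at (0.49 + 0.177)/1.177 = 56.7%.
- The long group is at 38.1% at 12 months, a difference of 18.6 points.
- Followed to 13 months, it is at 1 − 0.51^(√(13/12) − √(1/12)) = 39.7%, a difference of 16.9 points.

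**The per-protocol wording is no cure.** Read literally, Section 17 excludes any long-arm subject whose treatment stopped at an event before c + 12 months. Under the same null (constant hazard) the long arm then has 0% events by construction. The control arm, restricted to subjects event-free at c, has 46.1%, 39.6% or 28.6% at 12 months.

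**The case against.** The strongest objection is that the regrouping is inferred. No section says that subjects change group. Section 17, the only place that defines a set other than intent-to-treat, includes or excludes subjects and never moves them. Section 19 repeats the Synopsis text with per-protocol in place of as-treated, so the phrase may simply be unreconciled. This stands as far as it goes: the documents prove an undefined term and a contradiction, and the bias follows on the ordinary reading. Grouping by treatment started would move nobody, so the possible bias starts at zero. But that analysis would equal intention-to-treat and add nothing.

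A second objection concerns size. A reader might infer that the bias is as large as the planned 15-point effect (49% to 34%). With constant hazard, that holds only for c = 3 or 6 and only with both arms cut at 12 months. On the longer-of horizon that Section 6 uses, all three constant-hazard figures fall below 15 points. The values of c and the hazard shape are assumptions on either horizon. This objection stands, so the size is a range and not an estimate.

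A reader might also infer that the analysis favours long treatment whatever the drug does. Only the null case was worked out. At c = 1 month the constant-hazard bias is 2.6 to 5.6 points, which a modest harm could offset.

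Last, a reader might infer that the analysis could rescue a null trial. Section 17 makes intent-to-treat the primary analysis set for testing the primary endpoint, and the Synopsis calls the other analysis subsequent. It cannot change the formal conclusion, only how the results are read.

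The Section 6 clause on resuming the drugs does not remove the problem. Resumption comes after the event and rests on the provider's decision.

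**Conclusion.** The concern holds for a non-primary analysis. The Synopsis names an as-treated comparison that is undefined and conflicts with Sections 17 and 19. If groups are formed by duration received, the Section 6 stop rule lets the outcome decide the group and biases the comparison towards long treatment.

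Under no drug effect, constant hazard and c of 1 to 6 months, the bias runs from 2.6 to 11.3 points on the longer-of horizon and from 5.6 to 31.8 points at a 12-month cut. An early-loaded hazard would make it larger at a given c; a rule based on treatment started would make it zero. The documents fix none of c, the hazard shape or the grouping rule. The primary intention-to-treat result is untouched.

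**What to change.** Delete the as-treated analysis from the Synopsis and use one wording for the follow-on analysis in the Synopsis and Sections 17 and 19.

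For any adherence-based analysis, state two rules: subjects stay in their randomised arm, and stopping study treatment because of a primary event is not a departure from assigned duration. Do not simply copy the Section 17 definition into the Synopsis; amend it with the second rule.

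Two methods are available if more is wanted. One censors subjects at the first departure that precedes any primary event, with inverse-probability-of-censoring weights. The other sets a landmark at the end of the indicated duration and compares subjects still at risk, grouped as randomised. Both depend on the medication data recorded. Table 2 lists therapy assessment and concomitant medications at visits but does not mention stop dates, and it allows phone visits with laboratory values only where available. Check this before committing to either method.

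The cost is a wording change and a little analysis work. The core fix needs no new data; the weighted analysis might.

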#### **1. Introduction and Rationale**

Peripheral arterial disease (PAD) is extremely prevalent worldwide and affects over 206 million people. Over 36 million patients with PAD are estimated to be present in the United States. Percutaneous revascularization therapies have evolved dramatically, yet the long-term success of these therapies remains modest and the morbidity and mortality associated with PAD remains high, with up to 30% mortality risk at 5 years . Nearly, 3.2 million endovascular procedures are performed annually. Though, this exceeds interventional procedures performed for coronary artery disease (CAD), the current PAD guidelines are silent regarding the need and optimal duration of antiplatelet therapy (APT) for patients following an endovascular procedure for claudication or critical limb ischemia (CLI).  The lack of data and clinical studies is by far the greatest impediment to the formulation of such guideline recommendations critically needed by providers and patients alike, especially given the current limited durability of lower extremity endovascular procedures.

# 2. Clinical outcomes following lower extremity endovascular interventions

Endovascular or surgical revascularization procedures are performed on individuals with lifestyle-limiting claudication or CLI Percutaneous transluminal angioplasty (PTA) is a wellestablished endovascular technique for revascularizing obstructed lower limb arteries. This technique is associated with good patency in iliac artery interventions; however with dismal patency rates for infra-inguinal interventions.8 Stents have improved patency of lower extremity arterial interventions, mainly applied at the aortic bifurcation or in iliac segments. Until recently stents in the femoropopliteal district were associated with a higher risk of reocclusion because of the smaller diameter of these vessels. However, the new generation of self-expanding nitinol stents or paclitaxel-coated balloons have yielded better results than those obtained with standard balloons at the femoropopliteal level. Compared to surgical procedures, endovascular techniques are less invasive and are associated with lower morbidity and mortality and shorter recovery time. The main disadvantage of endovascular intervention is the low rates of long-term success, with relatively frequent clinical deterioration and restenosis during follow-up. Thus, reintervention is often necessary in patients treated with endovascular intervention for symptomatic with PAD. In addition to the type of intervention, early studies have demonstrated the impact of clopidogrel discontinuation on acute thrombotic occlusion of the limb post- endovascular intervention. In addition clopidogrel use in patients with PAD has been associated with improved mortality and non-fatal myocardial infarction (MI) events.

# **3.** Antiplatelet agents following lower extremity endovascular intervention

It has been shown that dual antiplatelet therapy is a very important factor for short- and longterm success in coronary interventions. Thus, based on the results of randomized clinical trials,

current guidelines recommend dual antiplatelet therapy consisting of clopidogrel and aspirin for 12 months after percutaneous coronary intervention (PCI) for acute coronary syndromes and/or use of drug-eluting stents.

After peripheral artery interventions, there is still some uncertainty regarding the optimal periand post-interventional antiplatelet treatment of clopidogrel and/or aspirin

.6 The results of the Management of peripheral arterial interventions with mono or dual antiplatelet therapy (MIRROR) study showed that patients treated with clopidogrel+aspirin compared to aspirin alone had significantly lower target lesion revascularization (TLR) rates at 6 months. Nevertheless, the duration of dual antiplatelet therapy remains unknown and not been addressed by well-powered randomized clinical trials. The investigators of the MIRROR study therefore conducted an additional clinical follow-up of MIRROR patients at 12 months to evaluate the persistence or extinction of the clinical advantage of dual antiplatelet therapy. At 6 months, clopidogrel patients had significantly lower rates of TLR compared to placebo patients [2 (5%) vs. 8 (20%), p=0.04]. None of the TLR was due to thrombotic occlusion of previously recanalized arteries. There were no significant differences in the rate of binary restenosis at 6 months. After stopping clopidogrel/placebo, the significant difference in TLR disappeared [9 (25%) clopidogrel vs. 12 (32.4%) placebo (p=0.35)]. Thus in contrast to the first report of a reduction in the TLR at 6 months in the MIRROR study, this advantage of dual antiplatelet therapy does not persist after stopping clopidogrel. The investigators concluded that prolonged dual therapy (>6 months) should be considered in patients who are at high risk for restenosis.

Peripheral catheter interventions are performed under local anesthesia allowing early and full mobilization. However, as a result of this intervention, atherosclerotic plaques are ruptured and platelets aggregate at the site of injury. Extensive vessel wall damage coupled with low shear stress and poor infrapopliteal outflow are mostly responsible for the occurrence of reocclusion.

Additionally, in the initial phase after catheter intervention, a hypercoagulable state prevails, as parameters of activated coagulation, including thrombin-antithrombin complexes (TAT), D-Dimer and Fibrinopeptide A (Fa) become elevated in the plasma. This activated coagulation system produces conditions favorable for early thrombotic occlusion, where 'early' is usually defined as a period covering the first four weeks after the intervention. Subsequently, intimal hyperplasia may follow which is responsible for intermediate and late-term restenosis and reocclusion. Intimal hyperplasia occurs as a result of denudation (tearing off of the inner lining) of the endothelium caused by manipulation of the vessel wall with the catheter. Reported rates of arterial reocclusion or symptomatic restenosis following femoropopliteal PTA are between five and twenty-five per cent for early events and about 40% one year. The five year patency rate was reported to be 83% for iliac and 58% for femoropopliteal PTA, whilst patients with stenoses or occlusions of less than 3 cm had a favorable long-term patency rate of 74%

Patients with CLI or those subjected to local thrombolysis show higher incidences of reocclusion. The implantation of drug-eluting or nitinol stents, or treatment by intravascular brachytherapy following PTA are considered as interventions with the capacity of reducing the occurrence of intimal hyperplasia, however may be associated with delayed endothelialization

and increased risk of thrombosis.

Drug interventions with antiplatelet agents to prevent thrombosis and/or reocclusion of the treated segments would make an important contribution to the sustained success of endovascular treatment, along with its contribution towards reducing overall mortality in patients with PAD. Current peri-interventional treatment strategies mostly include aspirin intake before and after PTA, initial administration of either unfractionated heparin (Ellis 1989) followed mostly by antiplatelet drugs or anticoagulants on a long-term basis (Do 1994; Hess 1985; Shammas 2003b; Watson 2000). However, these practices have never been tested in the setting of an adequately powered randomize controlled trial.

The Swedish trial on aspirin (50 mg daily) use after PTA was a negative study, whereas the study by Heiss et al showed greater patency and a dose effect favoring a higher dose of aspirin (100- 300 mg daily).24 At time points three and 12 months there were 798 and 575 patients included with OR 1.38 (95% CI 0.85 to 2.23) and 0.98 (95% CI 0.64 to 1.48), respectively, for primary occlusion. In fact, one clinical trial called CAMPER (Clopidogrel and Aspirin in the Management of Peripheral Endovascular Revascularization) (CAMPER) was started in the USA evaluating clopidogrel combined with ASA versus ASA after femoropopliteal angioplasty. Unfortunately, this study had to be stopped due to insufficient randomization numbers after one year.

## 4. Trial Objectives

To evaluate whether clopidogrel 75 mg QD on a background of ASA 81 mg/d for U.S. sites (75-100 mg/d for international sites) for clinically indicated duration with a minimum of 30 days or an additional 12 months will lead to an increased rate of primary patency, limb salvage, freedom form ischemic stroke and survival, in patients receiving endovascular treatment of PAD.

## 5. Trial hypothesis

We hypothesize that DAPT with ASA and clopidogrel administered for an additional 12 months after a clinically indicated duration following iliac, FP or BTK endovascular intervention will improve primary patency, limb salvage, freedom form ischemic stroke and survival, in patients with symptomatic PAD.

## 6. Trial endpoints

Clinical endpoints will be analyzed in all subjects who are enrolled, regardless of whether the trial treatment administered successfully completed for the desired duration. A subject will be considered enrolled in the trial when he/she is randomized to one of the treatment arms of the study. All endpoints are subject-based unless otherwise specified.

The primary endpoint is subject-based of the longer of a 12-month or end of study treatment endpoint of the first occurrence of index limb arterial occlusion, surgical intervention,

endovascular intervention, amputation of the affected limb (primary patency and limb salvage), MI, ischemic stroke or death (survival)

The secondary endpoints are subject-based on the longer of a 12-month or end of study treatment endpoints that include: (a) the first occurrence of any individual component of the primary endpoint, (b) the first occurrence of the following during follow-up: cardiovascular death, or MI, or ischemic stroke, or any amputation above the ankle and (c) severe bleeding defined according to the Global Utilization of Streptokinase and Tissue plasminogen activator for Occluded coronary arteries (GUSTO) classification

The tertiary endpoint is based on the longer of a12-month or end of study treatment moderate bleeding according to the GUSTO classification

Clinically indicated DAPT duration will be based on the longest pre-discharge following index peripheral intervention procedure DAPT duration. This will be determined based on: peripheral intervention device IFUs, preceding coronary intervention, acute coronary syndrome or other guideline-based clinical or device specific DAPT duration.

Study treatment will be discontinued at the first occurrence of a primary endpoint as defined in the table below. Patients, however, can resume taking aspirin, Clopidogrel, or both based on their provider's clinical decision.

Primary endpoint definition(s)	Secondary/Tertiary endpoint definition(s)
Occlusion of the target limb documented by any imaging procedure performed clinically	As described in section 6, except for:
any maging procedure performed ennearly	GUSTO bleeding criteria:
Any surgical or endovascular	1. Severe or Life-threatening: Intracerebral hemorrhage resulting in substantial
revascularization procedure on the index limb	hemodynamic compromise requiring treatment
Amputation above the ankle of the index	2. Moderate: Requiring blood transfusion but not resulting in hemodynamic
limb Death from any cause	compromise
Ischemic stroke: An episode of neurological dysfunction caused by focal cerebral, spinal, or retinal infarction confirmed by a neurologist	3. Mild: Bleeding that does not meet above criteria
MI: Detection of a rise in cardiac troponin	
(cTn) with at least one value 3x above the	
99th percentile upper reference limit (URL) and with at least 1 of the following:	
Symptoms of ischemia	
• New or presumed new significant ( $\geq 1$	
mm) ST- segment–T wave (ST–T)	
changes or new left bundle branch block (LBBB)	

• Development of pathological Q waves in the ECG	
--	--

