## 7. Trial design

This is a prospective, multi-center, two-arm randomized clinical trial to evaluate whether clopidogrel 75 mg QD on a background of ASA 81 mg for U.S. sites (75-100 mg/d for international sites) for clinically indicated duration with a minimum of 30 days or an additional 12 months will lead to an increased rate of primary patency, limb salvage and survival, in patients receiving endovascular treatment of PAD.

Up to 404 subjects at approximately 18 centers in the United States are planned. Assuming 10% attrition at 12 months, enrollment of a minimum of 404 would yield at least 368 evaluable subjects for the longer of a12-month or end of study treatment endpoint. No center will be allowed to enroll more than 40% of the subjects.

A schematic of the trial design is provided in Figure 1.

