## 14. Sample size estimate

The occurrence of the primary endpoint is expected to be approximately 49% in the control group, derived on the basis of current literature review and preliminary data form XLPAD registry.

A 30% relative risk reduction in the incidence of primary endpoint would be clinically important. To detect a 30% relative reduction in the primary event rate from 49% to34%  with 80% power at the two-sided, 0.05 significance level, assuming a 12-month recruitment period and a 10% dropout rate at 1 year, a total of 404 patients will be randomized (202in each group) and followed-up for endpoints for longer of a 12-month or end of study treatment period.

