## 17. Analysis set

The primary endpoint will be analyzed on an intent-to-treat basis and on a per-protocol basis analysis will also be performed. For intent-to-treat analysis, all subjects who sign the IRB/ECapproved written Informed Consent form and are enrolled into the trial will be included in the analysis, regardless of whether they receive the control or active arm drug treatments for the assigned durations or not. For per-protocol analysis, only subjects who receive the control or active arm drug treatments for the assigned durations will be included in the analysis.

The primary analysis set for testing of the primary endpoint is the intent-to-treat analysis set. No formal interim analyses are planned for the purpose of stopping this trial early for efficacy.

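### Bleeding is compared as randomised over windows that include time after the protocol-mandated treatment stop and differ in length between arms, and no on-treatment or post-divergence bleeding analysis is defined

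*Combined protocol and SAP*

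**What the plan says.** Section 6 sets one population for every clinical endpoint: "Clinical endpoints will be analyzed in all subjects who are enrolled, regardless of whether the trial treatment administered successfully completed for the desired duration". Severe GUSTO bleeding is a secondary endpoint and moderate bleeding the tertiary one. Both run to the longer of 12 months or end of study treatment. The synopsis instead heads the secondary endpoints as running to the end of study treatment, with no 12-month alternative.

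Section 6 also says: "Study treatment will be discontinued at the first occurrence of a primary endpoint as defined in the table below". The provider may then restart aspirin, clopidogrel or both, in either arm. Randomisation falls within two weeks of the procedure (synopsis). Under Section 9, both arms take DAPT for the clinically indicated duration, called c here (at least 30 days in control), and the test arm continues for 12 months more.

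On treatment-based analyses, Section 17 says: "The primary endpoint will be analyzed on an intent-to-treat basis and on a per-protocol basis analysis will also be performed". Section 19 announces a further per-protocol analysis and the synopsis an as-treated one. Neither names an endpoint or an exposure window. Section 19 compares discrete variables by chi-square.

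**The concern.** Bleeding is the main harm to set against any benefit of longer DAPT. The plan expects many subjects to be taken off study treatment by a primary event: "The occurrence of the primary endpoint is expected to be approximately 49% in the control group", and 34% in the test arm. A first-event endpoint stops counting at the event that stops the drug. Bleeding goes on being counted afterwards, when the assigned contrast has ended. For a safety endpoint, dilution towards no difference is the unsafe direction.

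Two further features affect the same comparison. Follow-up before c carries no contrast. And for c up to 12 months, the window is c+12 months in the test arm but 12 months in control. A proportion with a bleed therefore mixes treatment effect with length of observation.

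**Working it through.** **1. The plan's own figure.** Inputs from Section 14: 49% against 34%, two-sided 0.05, 80% power, 10% dropout.

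n = [1.96·√(2·0.415·0.585) + 0.8416·√(0.49·0.51 + 0.34·0.66)]² / 0.15² = 168.2.

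Continuity correction: (168.2/4)·[1 + √(1 + 4/(168.2·0.15))]² = 181.3, so 182 per arm and 364 in total. Then 364/0.9 = 404.4, against the stated 404 randomised. (Section 7 gives 368 evaluable, 184 per arm.) The event rates below are therefore the ones the trial was sized on.

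**2. Hazards.** λC = −ln(0.51)/12 = 0.0561 per month; λT = −ln(0.66)/12 = 0.0346 per month; ratio 0.617.

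**3. Assumptions not in the documents.** Constant hazards; λC in both arms before c, and λT in the test arm after c; c = 1, 3 or 6 months; bleeding rate 2 on DAPT and 1 off; no open-label DAPT after an event; full follow-up of c+12 months (test) and 12 months (control).

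**4. Mean months per test-arm subject.**
- Shared DAPT: a = (1 − e^(−λC·c))/λC
- On treatment after c: b = e^(−λC·c)·(1 − e^(−12·λT))/λT
- After the mandated stop: d = c + 12 − a − b

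Expected bleeds, in units of the off-DAPT monthly rate, are 2(a+b) + d in test and 12 + a in control.

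| c | a | b | d | test | control | crude count ratio | rate ratio |
|---|---|---|---|---|---|---|---|
| 1 | 0.97 | 9.28 | 2.74 | 23.256 | 12.972 | 1.79 | (23.256/13)/(12.972/12) = 1.65 |
| 3 | 2.76 | 8.30 | 3.94 | 26.059 | 14.761 | 1.77 | (26.059/15)/(14.761/12) = 1.41 |
| 6 | 5.09 | 7.01 | 5.89 | 30.107 | 17.094 | 1.76 | (30.107/18)/(17.094/12) = 1.17 |

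**5. Post-stop time alone.** Start the clock at c and follow both arms for 12 months. The on-treatment share is b/12 = 77%, 69%, 58%, so 23%, 31%, 42% is off treatment after a primary event. The ratio is 1 + b/12 = 1.77, 1.69, 1.58.

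**6. Shared period alone.** With no stop at events, the whole-window rate ratio is 24/(12+c) = 1.85, 1.60, 1.33. This period affects benefit too: (1 − e^(−λC·c))/0.49 = 11%, 32%, 58% of control 12-month primary events fall in it. With no effect before c, the test arm's 12-month event risk is 35.4%, 38.1% or 42.0% instead of 34%, and power at 184 per arm falls from 83% to 75%, 56% or 27%.

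**7. Unequal windows alone.** If DAPT had no effect on bleeding, the crude count ratio would still be (c+12)/12 = 1.08, 1.25, 1.50.

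**8. Sensitivity.** If every subject in both arms resumes DAPT after an event, the test arm bleeds at rate 2 throughout. Control is off DAPT only from c to its event: 7.76, 5.97 or 3.64 months on average. The rate ratio is then 2/[(24 − 7.76)/12] = 1.48, and likewise 1.33 and 1.18. If instead a test subject's window closes at month 12, or at the event if later, the rate ratios are 1.68, 1.47 and 1.26.

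**The case against.** An all-randomised analysis is the natural one for a comparison of treatment strategies, and it should stay. Bleeding is also adjudicated, reviewed six-monthly by the DSMB and assessed for drug relationship. The illustrated size depends on a bleeding ratio and values of c that the documents do not give. All of this stands, and it limits the point to one of added analyses.

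Three stronger readings are tempting, and the documents do not support them.

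- A reader might infer that the whole loss of contrast falls on harm and spares benefit. It does not. The shared DAPT period lies inside the primary-endpoint window, which runs from the index procedure. Only post-stop time is one-sided, and only against the first-event composite: the secondary efficacy endpoints in Section 6 use the same population and window as bleeding.
- A reader might infer that bleeding gets only the all-enrolled analysis. The synopsis and Section 19 announce as-treated and per-protocol analyses without restricting them to one endpoint, and the synopsis window differs from Section 6. What is missing is a definition for bleeding. The Section 17 per-protocol set would not supply one: it keeps only subjects treated for the full assigned duration, so it drops those stopped early.
- A reader might infer that the reported harm must be too small. On crude proportions the longer test-arm window works the other way, so the net direction is not fixed.

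**Conclusion.** The point holds as one about definition and interpretation. Post-stop time dilutes a bleeding rate comparison without touching the first-event primary endpoint, the shared period dilutes both sides, and unequal windows inflate crude bleeding proportions in the test arm. The planned chi-square therefore cannot be read as an estimate of the bleeding cost of 12 more months of DAPT.

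Under the stated assumptions, the loss that is specific to harm takes a true ratio of 2.0 to between 1.58 and 1.77. The larger fall in the whole-window rate ratio also contains the shared period. The crude ratio stays near 1.8 only because two distortions partly offset each other. All these sizes depend on the assumed c, bleeding ratio and open-label use. A sound correction is cheap, so the change should be made, but nothing here shows that the trial would understate bleeding overall.

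**What to change.** 1. Keep the all-randomised bleeding analysis, but report events per 100 patient-years or a time-to-event comparison over a follow-up window common to both arms.
2. Add one pre-specified, co-reported analysis starting at c, in subjects still on study and free of a primary event at c.
   - Test arm: count bleeds to the earliest of first primary event, actual stop of clopidogrel plus a fixed short lag, or end of the common window.
   - Control arm: count bleeds to the earliest of first primary event, start of open-label clopidogrel, or end of the common window. Do not censor control at its scheduled stop at c, which would leave almost no control person-time.
   - Give the rate ratio with 95% CI.
3. Show the primary endpoint from c on the same basis.
4. Reconcile the secondary-endpoint window in the synopsis with Section 6, and the as-treated and per-protocol statements in the synopsis, Section 17 and Section 19. For each, name the endpoints it covers.

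Cost: a few added tables. Drug stop and restart dates must come from the medication assessments in Table 2, which lists no stop date as such. Control follow-up ends at 12 months when c is 12 months or less, so the common window after c is only 12 − c months (11, 9 or 6 for c = 1, 3 or 6) unless control follow-up is extended.

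Downside: the on-treatment estimate is open to selection, which is why both analyses are shown. It will also be imprecise. At 184 per arm, with assumed control bleeding risks of 1% to 3% and a risk ratio of 2, power is only 12% to 28%, so the interval matters more than the test.
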